There is a global pandemic caused by the SARS-CoV-2 virus, which threatens the lives of many and the economic stability of the world. Therapeutic approaches are badly needed, and an orally available, well tolerated small molecule agent could play a critical part in preventing and ameliorating COVID-19.

People with COVID-19 who are or experiencing mild symptoms that do not require hospitalization have no proven option other than supportive care. The safety profile of camostat mesilate is well-established. It is generally safe and well-tolerated.

Furthermore, reducing viral shedding may decrease household and community transmission of SARS-CoV2. Thus, the risk to benefit assessment of treatment with camostat mesilate in the face of COVID-19 is clearly in favor of potential study subjects.

This study will assess the time course of cessation of viral shedding, and gather clinical benefit information, in patients with COVID-19 treated with camostat mesilate plus SOC as compared to placebo plus SOC. Data from this trial is expected to support a larger study which will demonstrate clinical benefit and serve as a pivotal trial for approval. The information gathered from this study will also help define the safety profile in this setting and enable expansion into other patient populations such as those who have been exposed but who are not yet ill. This could have a significant impact on public health.

2. Additional Inclusion/Exclusion Criteria

The below participant criteria is necessary for camostat mesilate in addition to criteria already stated above in the platform protocol:

Inclusion

1. If male, subject must fulfill one of the following criteria:
 - a. Be sterile (e.g., have had a vasectomy at least 6 months prior to Day 1 dosing), OR,
 - b. Agree not to donate sperm during the study and for seven days following the last dose of study medication, AND,
 - c. Agree to strictly adhere to the following contraceptive measures during the study and for seven days following the last dose of study medication:
 - i. Abstain from sexual intercourse
 - ii. Use a condom during sexual intercourse with a female of child-bearing potential. In addition, the female partner must use another form of contraception (e.g. intrauterine device [IUD], diaphragm with spermicide, oral contraceptives, injectable progesterone, or subdermal implants).
2. If female, subject must fulfill one of the following criteria:

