 - a. Be unable to bear children (have not had a period for \geq 12 consecutive months, have had her uterus or ovaries removed, or have had a tubal ligation), OR,
 - b. Must ensure that their male partner is incapable of fathering a child (e.g., has had a vasectomy at least 6 months prior to study entry), OR,
 - c. If she is of childbearing potential will strictly adhere to the following contraceptive measures during the study and for seven days following the last dose of study medication:
 - i. Abstain from sexual intercourse, OR,
 - ii. Must ensure that their male partner agrees to use a condom during sexual intercourse and agree to use an approved method of contraception (e.g., IUD, diaphragm with spermicide, oral contraceptives, injectable progesterone, or subdermal implants).
 - d. Agrees to stop breast-feeding prior to first dose of study drug and through seven days after completing therapy.

Exclusion

1. Subject has received their first dose of any COVID-19 vaccine greater than 10 days prior to their Day 1 visit.
2. Subject is eligible for monoclonal antibody treatments for COVID-19 under EUA (see "NOTE" in Master protocol under section 3.2 for further details).
3. Subject has a history of gout or coagulation disorders.

4. Subject has a concomitant bacterial respiratory infection as documented by a respiratory culture with microbiologic growth.

NOTE: Subjects on empirical antibiotic treatment for possible but unproven bacterial pneumonia, but who are positive for SARS-CoV-2, are allowed in the study.

5. Has previously received camostat mesilate within the past 30 days.

Note: Clinical screening laboratory evaluations will be performed locally by the site or site-designated laboratory.

3. Camostat Treatment

Standard Dose

Subjects randomized to active camostat mesilate will receive 200mg one hour before meals (breakfast, lunch, and dinner) and before bedtime, for 800mg total in a day over 4 dosing periods. Those under the placebo group will receive inactive placebo.

Day 1 is deemed to be the first 24 hours after enrollment into the study, with time 0 (time of first dose) occurring as soon as possible after the subject's eligibility has been confirmed.

Administration of Camostat mesilate or placebo

The tablets will be dispensed in appropriately sized amber prescription containers with child-resistant caps. The prescription container and caps are manufactured from PP (polypropylene plastic).

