- The subject is unwilling or unable to comply with the safety procedures.
- The subject is discovered to be pregnant.
- The subject experiences a medical emergency that necessitates withdrawal.
- The subject is withdrawn at the discretion of the Investigator for medical reasons or non- compliance.
- AST or ALT > 8 x ULN
- ALT or AST > 3 x ULN AND total bilirubin > 2X ULN
- AST or ALT > 3 x ULN AND patient has right upper quadrant pain or eosinophilia
- Hypersensitivity
- Shock or anaphylactoid symptoms
- Absolute neutrophil count <800 cells/mm³

- Hemoglobin <11 g/dL for women and <12 g/dL for men
- Serum creatinine concentration $\geq 1.5 \times$ ULN
- Confirmed creatinine clearance (CrCl) < 50 mL/min by Cockcroft-Gault
- Platelet count <75,000 cell/mm³.
- Hepatic function disorder or jaundice (both incidences unknown).
- Hyperkalemia (incidence unknown). Severe hyperkalemia may occur.

A subject whose treatment is terminated should remain in the study for appropriate follow up assessments whenever possible.

Day of study	1	2	3	4	5 ±1	6	7	8	9	10 ±1	14	21	28 +7	120 ±7	210 ±7	300 ±7
Assessments in the clinic	X				X					X			X			
Physical exam	X				X					X			X			
Vitals	X				X					X			X			
Clinical status	X				X					X			X			
SpO2	X				X					X			X			
Urine Pregnancy Test	X															
Self-collected nasal swab	X	X	X	X	X	X	X	X	X	X	X	X	X			
COSS self-assessment	Every day from days 1-28 inclusive												X	X	X	
Oropharyngeal swab	X				X					X			X			
Blood collected by phlebotomy for clinical labs	X				X					X			X			
Blood collected by phlebotomy for biobanking	X ¹												X ¹			
Blood collected by phlebotomy for PK					X ¹											
Telehealth visit														X	X	X ²
Administration of drug - Camostat sub-protocol	X	X	X	X	X	X	X	X	X	X						

1-Denotes optional assessment for sites external to Stanford University.

2-Denotes additional telehealth visit if needed for following any ongoing AEs.

4. Known product related Adverse Events

Clinically Significant Adverse Reactions

As indicated on the FOIPAN label (Japanese approved product), the below listed clinically significant adverse reactions may occur. Patients should be carefully monitored. If any abnormalities are observed, appropriate measures such as discontinuing the administration should be taken.

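### Inclusion 2a treats 12 months without a period, whatever the cause, as inability to bear children, which conflicts with the contraception duties in 2c

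*Combined protocol and SAP*

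**What the plan says.** Section 2 (Additional Inclusion/Exclusion Criteria) introduces inclusion 2 with "If female, subject must fulfill one of the following criteria". The items are:

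- **2a** covers women unable to bear children, which its parenthesis spells out as "have not had a period for \geq 12 consecutive months", removal of the uterus or ovaries, or tubal ligation. It sets no age limit, does not mention menopause and does not exclude other causes of absent periods.
- **2b** covers women whose male partner cannot father a child.
- **2c** reads "If she is of childbearing potential will strictly adhere to the following contraceptive measures", and the duty runs through the study and for a week after the final dose. She must either abstain (2c(i)) or have a partner who uses a condom and also use an approved method (2c(ii)). The examples of approved methods are "IUD, diaphragm with spermicide, oral contraceptives, injectable progesterone, or subdermal implants".
- **2d** reads "Agrees to stop breast-feeding prior to first dose of study drug", and also runs until a week after therapy ends.

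The section states that its criteria apply "in addition to criteria already stated above in the platform protocol". The platform protocol is not among the documents supplied.

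The schedule in Section 3 has one row for "Urine Pregnancy Test X", marked on Day 1 only. Pregnancy is among the listed reasons for ending treatment or participation.

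**The concern.** The sponsor decided that women who could conceive should use contraception while in the study and for a week after dosing. Item 2a decides who is released from that duty, and part of its test is a symptom, the absence of periods, rather than inability to conceive. A woman can go 12 months without a period and still be fertile, or become fertile again soon.

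At stake is participant protection: some women whom the contraception rule was meant to cover would be released from it by this sub-protocol's wording. There is also a consistency problem, because a site following the text would handle two women with the same fertility and the same method differently. The trial's efficacy conclusions are not affected.

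**Working it through.** No arithmetic applies. The check is a reading of how the items of inclusion 2 combine.

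1. **One item is enough.** The lead-in asks for one of the listed items, and 2a and 2b each end with OR. A woman who satisfies 2a has met inclusion 2, and nothing in this sub-protocol then sends her to 2c.

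2. **The parenthesis in 2a reads as a definition.** Items 2b and 2c(ii) mark their lists as examples with e.g.; 2a does not. The natural reading is that any one of the three listed conditions makes a woman unable to bear children for this purpose. Twelve months without a period is one of them, on the same footing as surgical removal or tubal ligation.

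3. **Set 2a beside 2c(ii).** It is general clinical knowledge, not something the documents state, that injectable progesterone, implants and some uses of oral contraceptives or IUDs can stop periods. Take two women on the same injection, neither with a partner covered by 2b:
   - Woman A still has periods. She does not meet the 12-month condition. Under 2c she must abstain, or keep to her method strictly and have her partner use a condom.
   - Woman B has had no period for 12 months because of the injection. She meets 2a. She need not abstain, add a condom or continue the injection.

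   The conflict exists even if Woman B never misses an injection, because the sub-protocol does not accept the injection alone as sufficient for Woman A.

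4. **Set 2a beside 2d.** Item 2d expects that some women will be breast-feeding at entry. As an illustration, about nine months of pregnancy plus three months without a period afterwards is 9 + 3 = 12 months, which meets the condition in 2a. Such a woman has recently shown that she can bear children, yet 2a would class her as unable to.

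5. **Item 2d has a related fault.** It is the fourth item under the same lead-in, and no connective joins it to 2c. Read literally, agreeing to stop breast-feeding would satisfy inclusion 2 on its own. Its content suggests that it was meant as an extra condition.

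6. **Look for another rule that closes the gap.** Nothing else in the sub-protocol requires contraception of a woman who qualifies under 2a. The Day 1 urine test can detect a pregnancy already present at entry. It cannot prevent a later one, and no later test is scheduled.

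**The case against.** The strongest objection is that this document is an add-on. Platform criteria apply as well, and exclusion 2 refers the reader to Section 3.2 of the master protocol. A platform definition of childbearing potential, or a platform contraception rule, could already cover these women. This stands as a limit: the point is established for the sub-protocol's text only. It does not remove the point, because a stricter platform rule would then disagree with 2a and the two would still need aligning.

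A second objection is that the governing words of 2a are about inability to bear children, and that 2c speaks of any woman of childbearing potential. A sensible site would put a young woman on injectable progesterone under 2c. Some would. But 2a supplies its own list with no sign that it is only illustrative, and the sub-protocol does not define childbearing potential anywhere else. A coordinator who follows the text can record her under 2a.

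Third, most women in the hormonal group are already protected by the method that stopped their periods. This stands in large part. What they are released from is the condom and the duty to continue the method, so actual exposure requires a lapse or failure of the method. It would be wrong to describe the whole group as unprotected.

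Finally, a reader might infer from the single Day 1 test that a pregnancy conceived on study would be missed. The documents do not support that. They show only that no later test is scheduled. Clinic visits with a physical examination take place on Days 5, 10 and 28, and removal for pregnancy does not depend on a scheduled test. The testing schedule also makes no distinction between women under 2a, 2b and 2c, so it is not a fault of 2a.

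**Conclusion.** The point holds for the text of this sub-protocol. Item 2a releases from contraception any woman with 12 consecutive months without a period, whatever the cause, and this conflicts with 2c. Item 2d sits in the list as an alternative when it appears to be meant as an additional condition.

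The size cannot be calculated. The documents do not say how many women would qualify under 2a for a reason other than menopause or surgery, and they contain no reproductive-toxicity data from which to judge the consequence. The number is probably small, and many of those women are already using a method.

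The conclusion assumes that the list in 2a is a closed definition, and that hormonal methods and the months after childbirth can produce long absence of periods. A reader might go further and conclude that the trial as a whole exempts fertile women from contraception. That does not follow, because the platform protocol also applies and may be stricter. The wording is worth correcting, with modest priority.

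**What to change.** Reconcile 2a with 2c and with the platform protocol:

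- Limit the 12-month condition to women who are actually unable to bear children, meaning that the absence of periods is not explained by another cause such as hormonal contraception or lactation. All other women then fall under 2b or 2c.
- Move 2d out of the list of alternatives and state it as a separate requirement, so that it cannot satisfy inclusion 2 on its own.
- Confirm that the platform protocol's definition of childbearing potential, if it has one, says the same thing.

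The surgical conditions in 2a need not change for this purpose. The cost is a one-line change to 2a, the relocation of 2d and a matching edit to the screening form. No test or visit is added. A few reclassified women would have to meet 2b or 2c. For those relying on 2c(ii), that means the partner's condom as well as their existing method.

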Camostat mesilate is provided as 100 mg tablets and dosed orally. Subjects will be instructed to take their doses at least two hours after a meal and one hour before the next meal, and at bedtime

Subjects who vomit during or immediately after dosing, should not be re-dosed.

Outpatient Camostat mesilate Dosing

Subjects in the camostat mesilate + SOC arm, will be dispensed sufficient camostat mesilate to ensure continued dosing until their next study visit.

Subjects will also be instructed that if they miss a dose, they should follow the guidelines:

- 1) If more than 1/2 the time until their next dose has elapsed, they SHOULD NOT take the dose. They should just take the next dose at the normal scheduled time.
- 2) If less than 1/2 the time until their next dose has elapsed, they should take the missed dose immediately.
- 3) In both cases, they should then return to their regular dosing schedule.

Drug Accountability

The Investigator must maintain adequate records showing the receipt, dispensation, or other disposition of camostat mesilate including the date, quantity and identification of subjects (study ID) who received camostat mesilate. Drug supplies will be inventoried and accounted. Unused supplies of all camostat mesilate will be returned to the Sponsor or destroyed on site in accordance with local procedures upon approval of the Sponsor.

Treatment Compliance

The pharmacy will provide bottles of camostat mesilate for outpatient use (Exact dispensing instructions for outpatients will be described in the pharmacy instructions). Assessment for compliance with each dose will be monitored and recorded in accordance with site standard operating procedures. During the days 5 and 28 in-person visits, participants will be asked to bring their prescribed medication with them to track participant compliance.

Management of Progression of Disease

Should the patient be admitted to the hospital, they will follow protocol for inpatient procedures at the hospital, which usually includes the IV antiviral drug remdesivir. The clinical team for the patient will make a recommendation as to whether drug must be stopped or unblinded.

Removal of Subjects from Treatment

The participation of a subject in the study or the administration of treatment may be terminated at any time for one of the following reasons:

- The subject desires to discontinue study treatment.
- The subject withdraws consent to participate in the study.

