- Shock or anaphylactoid symptoms (both incidences unknown). If any symptoms such as decreased blood pressure, dyspnea, and pruritus are observed, administration should be discontinued and appropriate measures be taken.
- Thrombocytopenia (incidence unknown).
- Hepatic function disorder or jaundice (both incidences unknown).
- Hepatic function disorder accompanied by remarkable increase of AST (GOT), ALT (GPT), γ -GTP, Al-P, or jaundice may occur.
- Hyperkalemia (incidence unknown). Severe hyperkalemia may occur.

Other Adverse Reactions

Incidence ¹ /Adverse Reaction	0.1%-0.5%	<0.1%	Unknown
Hematologic		Leukopenia, erythrocytopenia	Eosinophilia
Hypersensitivity ²	Rash, pruritus		
Gastrointestinal	Nausea, abdominal discomfort, abdominal fullness, diarrhea	Anorexia, vomiting, dry mouth, heartburn, abdominal pain, constipation	
Hepatic	Increased AST (GOT), ALT (GPT), etc.		
Renal		Increased BUN, increased creatinine	
Other		Edema, hypoglycemia	

¹ The incidences are calculated by including reports from the drug use surveillance

² If such symptoms are observed, administration should be discontinued.

Prohibited Concomitant Therapy

The following may interact with camostat mesilate and risks and benefits should be carefully considered prior to treatment with the following:

- Any other anti-viral medication whether investigational or approved.

5. Additional Endpoints (Safety, Secondary, and Exploratory)

Safety will be assessed by the collection of observed and reported adverse events, physical exams, vital signs and the following clinical laboratory tests:

- **Hematology**

Hemoglobin (Hgb)	Hematocrit (Hct)
Platelet count	Red blood cell count
White blood cell count with differential	

- **Chemistry**

Blood Urea Nitrogen (BUN)	Creatinine
Total bilirubin	Alkaline Phosphatase
Aspartate transaminase (AST)	Alanine transaminase (ALT)
Glucose	Lactic dehydrogenase (LDH)
Total protein	Albumin
Potassium	Bicarbonate
Calcium	Sodium
Urate	Chloride
	C-reactive protein

Resistance testing, as required in clinical trials of anti-viral drugs will be performed at each time point that oropharyngeal swabs are taken.

Pharmacokinetic testing will be performed at day 5. Participants will be asked to take their dose in the clinic on day 5 for their in-person appointment. PK testing to sites external to Stanford University are optional.

Additional secondary endpoint:

- 1) To evaluate the proportion of individuals with a negative SARS-CoV2 RT-PCR test on days 14 and 28

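### Should the returned-medication check also be made at the Day 10 clinic visit, when dosing ends?

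*Combined protocol and SAP*

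**What the plan says.** The Treatment Compliance paragraph of section 3 makes two provisions. The general one is "Assessment for compliance with each dose will be monitored and recorded in accordance with site standard operating procedures". It covers every dose and leaves the method and timing to the site. The specific one ties a check to named visits: "During the days 5 and 28 in-person visits, participants will be asked to bring their prescribed medication with them to track participant compliance".

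Under Drug Accountability in the same section, the investigator keeps dated records of quantities received and dispensed, and "Unused supplies of all camostat mesilate will be returned to the Sponsor or destroyed on site". No time is set for the return. Drug is dispensed from one study visit to the next.

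The regimen under Standard Dose is 200 mg four times daily, "for 800mg total in a day over 4 dosing periods". In the schedule of assessments, the row "Administration of drug - Camostat sub-protocol" is marked on each of Days 1 to 10. The same schedule has clinic visits on Day 1, Day 5 ±1, Day 10 ±1 and Day 28 +7. Section 5 says "Pharmacokinetic testing will be performed at day 5"; that sample is optional at sites outside the lead centre.

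**The concern.** Day 10 is the clinic visit nearest the end of treatment, and it is the only clinic visit after baseline at which participants are not asked to bring their medication. The supply handed out at Day 5 is meant to last until the next visit, so Day 10 looks like the natural time to count what is left. Instead, the second half of the course (roughly) is first compared with returned tablets at Day 28 or later. By then a participant may have discarded the bottle or left the study. The PK sample does not help, because it is drawn at Day 5 and says nothing about later doses.

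At stake is the reading of a null result. If camostat showed no effect, the sponsor would want to know whether the drug failed or was not taken. For a participant with no bottle at Day 28, the only evidence on the later doses would be whatever the site's own procedures had recorded.

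**Working it through.** **Inputs** (section 3 and the schedule of assessments): four doses of 200 mg a day; 100 mg tablets, so 2 per dose; dosing on Days 1 to 10; visit windows Days 4 to 6, Days 9 to 11 and Days 28 to 35.

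**Stated figure.** 4 × 200 mg = 800 mg a day, which agrees with the plan.

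**Size of the course.** 4 × 10 = 40 doses, or 40 × 2 = 80 tablets. This takes four doses on Day 1, which fits the definition "Day 1 is deemed to be the first 24 hours after enrollment into the study".

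**Doses after the first check.** For a visit on day v, the number lies between 4 × (10 − v), if all that day's doses have been taken, and 4 × (10 − v + 1), if none have.

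| First visit on | Doses still to come | Share of 40 |
|---|---|---|
| Day 4 | 24 to 28 | 60% to 70% |
| Day 5 | 20 to 24 | 50% to 60% |
| Day 6 | 16 to 20 | 40% to 50% |

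The full range is 16 to 28 doses (32 to 56 tablets). The value 28 is an outer limit: it needs a Day 4 visit before any dose that day, and becomes 27 if one dose is taken in clinic at that visit.

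**Delay to the next visit-specified check.** 28 − 10 = 18 days; 35 − 10 = 25 days.

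**What a Day 10 check would add.** Doses not yet taken would number 4 to 8 at a Day 9 visit, 0 to 4 at Day 10 and 0 at Day 11. The check would therefore cover 32 to 40 of 40 doses (80% to 100%), and Day 28 would still be needed for the remaining 0 to 8.

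**What the Day 28 check already covers.** Every dosing day precedes Day 28, so a participant who brings all remaining medication allows the whole course of 40 doses to be reconciled. Leftover tablets do not change in number between Day 11 and Day 28, so delay in itself removes nothing. Let f be the proportion of participants with no medication to show at Day 28. The average share of the course without a returned-medication check is then f × (40% to 70%): zero if f = 0, and 40% to 70% only in the extreme case f = 1. The document does not give f.

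**What depends on it.** The interim and futility rules in section 8 use a Wald test on the hazard ratio from the primary Cox model. The additional secondary endpoint in section 5 is the proportion PCR-negative on Days 14 and 28. Neither uses a compliance measure, and the supplied text describes no adherence-adjusted or per-protocol analysis. Adding the check changes no stated quantity.

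**The case for a change.** The best case for adding Day 10 is that it is cheap and that exposure matters here. By the plan's own account, plasma levels at 200 mg only just reach the inhibitory range, and the active metabolite's half-life is about 100 minutes, so missed doses could blunt an effect. The regimen is demanding: four times a day, timed around meals. The results are meant to inform a larger study, so explaining a null result has value. The site-procedures sentence gives no method, so practice may vary between sites. The visit already exists, and one more count would take little effort.

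Most of this stands as an argument for good practice: a count close to the last dose is better evidence than one made weeks later. It does not show a fault in the plan. The sentence on site procedures is a protocol requirement that covers doses after Day 5, so those doses are not left unmonitored. The text supplied is a drug-specific sub-protocol, and it refers to a platform protocol and to pharmacy instructions that are not included. Either may contain a Day 10 count or a diary. The cost is also somewhat more than one word, because sites would have to record doses still due and avoid collecting bottles while doses remain. By Day 10 the course is nearly over, so the count would come too late to improve adherence during it.

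**Conclusion.** The facts are right, but no change is needed. The sub-protocol names Days 5 and 28 for bringing medication back and leaves out Day 10, so 16 to 28 of 40 doses wait until 18 to 25 days after the last scheduled dosing day for that particular check. This is a limit on how promptly adherence is documented. It does not leave those doses without a check, because recording of each dose is separately required and the Day 28 check comes after the whole course.

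A trial run exactly as written would reach the same results and conclusions. A Day 10 count would make the adherence records more complete for participants who later lose their bottles or miss Day 28, and a sponsor could adopt it as a matter of site practice.

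The conclusion rests on three assumptions: four doses are taken on Day 1; sites carry out the per-dose recording that the sub-protocol requires; and no adherence-based analysis sits in the platform documents. If such an analysis did exist, the completeness of the later counts would deserve a second look.
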